9.5 Modeling of the Primary Endpoint

Tests of hypotheses for a one-sample proportion described in 9.4 will calculate the variance of the proportion using a normal approximation to the binomial distribution with PROC FREQ. As noted in 9.8.4, the analysis is repeated in each imputed data set and thereafter aggregated. Once aggregated, inference will be based on the lower bound of the 95% confidence interval.

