## 7.8 Sample Size Justification

The sample size was determined based on the primary endpoint using the one-sample exact-test of a proportion as implemented in PROC POWER in SAS, version 9.3 or higher. For the calculation, we assume the composite success proportion at 24 months after surgery is 85% and implement a one-sided test at the 0.025 alpha-level to determine the minimal N which provides more than 80% power; this sample size is 133. To accommodate potential 15% attrition, the sample size will be increased to 157.

The sample size applies to patients enrolled and actually treated. Some patients who were enrolled in a study may not be ultimately treated for various reasons. Patient enrolment will continue until the proposed sample size for treated patients is complete.

**NOTE:** Although the sample size was originally determined based on the anticipated use of a one-sample exact-test of a proportion, it has been determined after enrolment was complete that a one-sample Z-test of a proportion using a normal approximation would be utilized in the final primary endpoint analysis to facilitate data imputation methods.

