### 7.9.1 Primary Endpoint

The primary endpoint is a composite success at 24 months post-operatively. The components of this endpoint characterizing success consist of all of the following: 1) based on two-year post-operative radiographs, there is no continuous radiolucent line around the GLOBAL ICON stemless humeral component, 2) Two-year post-operative adjusted Constant-Murley Score  $> 85$ , 3) absence of component removal, and 4) absence of serious adverse events related to the device. The primary endpoint analysis will be conducted on subjects who are in the Safety population. As described in Section 7.4 Interval Windows will be implemented for the primary endpoint analysis.

The primary endpoint analysis will be conducted using a one-sample Z-test of a proportion using a normal approximation, with multiple imputation methods as described in the SAP to account for missing data.

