Only the primary objective for the endpoint of device success is prospectively powered and will be conducted with a one-sided test of $\alpha = 0.025$, or equivalently, whether the lower bound of the 95% confidence intervals is above the maximum value under the null hypothesis. Confidence intervals (two-sided 95%) and p-values may be provided for analyses involving the primary, safety, secondary and tertiary endpoints. For safety endpoints no hypotheses will be tested, and the secondary/tertiary objectives are deemed exploratory. In light of these considerations, there will be no adjustment of significance levels because of testing multiple hypotheses. No labeling claims will therefore be made based on the analysis of safety, secondary and tertiary endpoints.

7. Analysis Sets

Analysis set definitions from the CIP appear below.

Consented/Enrolled Population: The Consented/Enrolled Population will consist of all subjects who were consented and enrolled in the study based on preliminary subject eligibility.

Safety Population: The Safety Population will consist of all subjects who were enrolled and were either implanted with the GLOBAL ICON stemless humeral component or an attempt was made to do so. Demographic data and analysis of the primary, safety, secondary and tertiary endpoints will be based on the Safety Population.

Per Protocol Population: The Per Protocol Population will consist of the subset of the Safety Population without specific protocol deviations. Based on review of subject data, the subset will exclude those patients that: 1) fail to satisfy all inclusion/exclusion criteria, 2) received a non-Global ICON humeral component or did not receive an approved DePuy Synthes glenoid system, and 3) failed to adhere to critical protocol-required restrictions and prohibitions, receipt of prohibited concomitant procedures or therapies, and severe non-compliance to protocol-specific procedures. The final Per Protocol Set will be determined prior to database hard lock and in agreement with clinical research and clinical operations. Analyses using the Per Protocol Population will be used to complement analyses based on the safety population.

8. Sample Size Justification

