9.4 Hypothesis Testing of Primary Endpoint

The primary endpoint analysis will seek to demonstrate that at the 24 month visit after surgery, the composite success (p), which is based on four study outcomes (radiograph demonstrating no continuous radiolucent line around the humeral component, adjusted Constant-Murley Score > 85, no removal of the humeral component, no serious adverse events related to the device), is significantly greater than a performance goal (PG) of 75%. The null and alternative hypotheses for this endpoint are as follows:

Null hypothesis H_{01} : $p \leq 75\%$

Alternative hypothesis H_{A1} : $p > 75\%$

The null hypothesis will be rejected and the alternative hypothesis will be accepted if the lower bound of a two-sided 95% confidence interval is greater than 75%. The performance goal of 75% used in the hypothesis test described above is based on the percentage of successful stemmed implants at the 24 month visit reported elsewhere using a similar definition of success [4]. Therefore, the hypothesis test implies a comparison to performance of stemmed implants. In a prior study, non-inferiority of the Simpliciti stemless humeral device to stemmed devices was demonstrated using a PG of 65% (75%-10% non-inferiority margin) [4]. Therefore, the current study sets a higher bar to establish successful performance of Global Icon when compared to the study evaluating the Simpliciti device.

Another objective using the same endpoint is to establish non-inferiority of Global Icon to Simpliciti conditional on rejection of H_{01} . To do so a PG or non-inferiority margin of 78.74% (Simpliciti success percentage of 88.74% [5] -10%) is selected. The null and alternative hypotheses for this objective are as follows:

Null hypothesis H_{02} : $p \leq 78.74\%$

Alternative hypothesis H_{A2} : $p > 78.74\%$

The null hypothesis will be rejected and the alternative hypothesis will be accepted if the lower bound of a two-sided 95% confidence interval is greater than 78.74%. Notably,

simultaneous testing of these nested null hypotheses (H_{01}, H_{02}) does not inflate the Type I error rate [6,7].

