9.5.1 Adequacy of the Normal Approximation

A reasonable concern is that the success proportion will be close to 1 in this study, and it is unclear how well the normal approximation performs in this case. Using Monte Carlo simulation, performance of the normal approximation was evaluated. We generated 100,000 replications with either no missing data or 15% missing data (under a missing completely at random mechanism) with values that were subsequently imputed (10 imputations) using methods described elsewhere [8]. The population success proportion was set at 0.90 with 157 observations in each replication. Both in the absence of missing data and in the presence of missing data, the normal approximation yielded slight under-coverage relative the nominal level of 95%, 94.5% and 94.0%, respectively. By comparison, the Wilson method yielded slight over-coverage, 95.6% and 95.2%. Given these results, the normal approximation was chosen.

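### The Wald lower confidence bound that decides both success claims runs at about 3.3% and 3.8% one-sided error (complete data, n=157), not the stated 2.5%

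*SAP*

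**What the plan says.** SAP 6 powers only the primary objective, at one-sided 0.025, and describes the test as interchangeable with checking "whether the lower bound of the 95% confidence intervals is above the maximum value under the null hypothesis". SAP 9.4 applies that rule twice: H01 against 75%, then H02, which is rejected if the "lower bound of a two-sided 95% confidence interval is greater than 78.74"%.

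SAP 9.5 will "calculate the variance of the proportion using a normal approximation to the binomial distribution with PROC FREQ", repeat this in each imputed data set and pool the results, after which "inference will be based on the lower bound of the 95% confidence interval". Protocol 7.9.1 agrees: "The primary endpoint analysis will be conducted using a one-sample Z-test of a proportion using a normal approximation".

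The sample size in Protocol 7.8 and SAP 8 was built on an exact test. Both sections disclose that it was "determined after enrolment was complete that a one-sample Z-test of a proportion using a normal approximation would be utilized", and give ease of imputation as the reason.

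SAP 9.5.1 defends the choice by simulation at a true success rate of 0.90 with 157 observations. Without and with 15% missing data, "the normal approximation yielded slight under-coverage relative the nominal level of 95%, 94.5% and 94.0%, respectively". Wilson gave 95.6% and 95.2%. The section ends: "Given these results, the normal approximation was chosen".

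**The concern.** The success decision uses one tail of the interval only. A Wald interval for a proportion well above one half misses unevenly: its lower bound is too high more often than its upper bound is too low. Two-sided coverage adds the two misses together, so a figure near 95% can go with a lower-tail error well above 2.5%. SAP 9.5.1 reports only that combined figure, and gives no rejection rate at 0.75 or 0.7874, where type I error is defined.

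Both performance-goal claims rest on this bound. Protocol 7.10 says that the primary analysis will support a US marketing application. The move away from the exact test came after enrolment was complete and lowers the bar slightly. A result that passes by one success would therefore be open to challenge on the plan's own alpha.

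**Working it through.** **Inputs.** One-sided alpha 0.025 (SAP 6, SAP 8); p0 = 0.75 and 0.7874 (SAP 9.4); assumed success 0.85, evaluable N = 133, 15% attrition, total 157 (SAP 8); coverage check at p = 0.90, n = 157 (SAP 9.5.1); 50 imputations (SAP 9.8.4).

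**Step 1: reproduce the plan's figures.**
- Exact test at n=133: reject at 110 or more successes; P(X≥110 | 0.75) = 2.23%; power P(X≥110 | 0.85) = 80.8%. Attrition: 133/0.85 = 156.5, rounded up to 157. The power requirement is first met at n=132 (81.8%), a one-subject difference with no bearing here.
- Exact enumeration at n=157, p=0.90 gives two-sided coverage of 94.46% for Wald and 95.55% for Wilson, matching the SAP's complete-data 94.5% and 95.6%. This confirms that the SAP's normal approximation is the Wald interval.

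**Step 2: split the coverage by tail.** At n=157, p=0.90, the Wald miss is 4.20% on the lower bound and 1.34% on the upper, 5.54% in total. The choice of 0.90 was not flattering to Wald: the lower-bound miss is larger there than at either null value. The difficulty is that the combined quantity was reported.

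**Step 3: exact type I error of the planned rule.** The cut-off is the smallest r for which r/n − 1.96·√[(r/n)(1 − r/n)/n] exceeds p0. The error is P(X≥r | n, p0).
- H01, n=157: 128/157 = 0.8153, SE = 0.03097, lower bound 0.7546; 127 gives 0.7474 and fails. P(X≥128 | 0.75) = 3.31%.
- H02, n=157: 133/157 = 0.8471, SE = 0.02872, lower bound 0.7908; 132 gives 0.7835 and fails. P(X≥133 | 0.7874) = 3.79%.

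Testing H01 first does not reduce the H02 error, because every count of 133 or more also rejects H01.

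**Step 4: compare the limits (complete data).**

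| | Wald | Wilson | Exact (Clopper-Pearson) |
|---|---|---|---|
| H01, n=157: cut-off, error | 128, 3.31% | 129, 2.09% | 129, 2.09% |
| H02, n=157: cut-off, error | 133, 3.79% | 134, 2.34% | 134, 2.34% |
| H01, n=133: cut-off, error | 109, 3.65% | 110, 2.23% | 110, 2.23% |
| H02, n=133: cut-off, error | 113, 4.56% | 114, 2.74% | 115, 1.56% |
| H01, n=130–160: range (mean) | 2.8–4.5% (3.6%) | 1.7–2.8% (2.2%) | at most 2.49% |
| H02, n=130–160: range (mean) | 3.0–4.7% (3.8%) | 1.6–2.7% (2.1%) | at most 2.49% |
| Sample sizes above 2.5%, of 31 (H01; H02) | 31; 31 | 7; 5 | 0; 0 |

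A 1/(2n) continuity correction to Wald leaves both cut-offs at n=157 unchanged. It helps at some other sizes, but still averages 2.9% (H01) and 3.1% (H02) over n=130–160.

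**Step 5: with imputation (illustrative).** Setting: n=157, 15% missing completely at random, 50 imputations from a Beta(x+0.5, n_obs−x+0.5) draw, where x successes are seen among n_obs observed subjects, pooled by Rubin's rules. Wald rejected a true H01 in 3.5–3.6% of replicates and a true H02 in 3.7–4.0% across separate runs. Wilson gave 2.1% for each. This is a single-variable imputation; the fully conditional model in SAP 9.8.4 and 9.8.5 was not simulated.

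**The case against.** **The choice is disclosed.** SAP 9.5.1 raises the concern itself, prints the Wald shortfall beside Wilson and then chooses; the timing of and reason for leaving the exact test are also stated. That is fair, but what is disclosed is two-sided coverage at 0.90. The one-sided error at the two null values is not, and SAP 6 states that it is 0.025.

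**The effect is small.** This stands. With complete data at n=157, the H01 verdict differs only at exactly 128 successes, which has probability 4.1% at a true rate of 85% and 0.05% at 90%. For H02 (exactly 133) the figures are 8.8% and 1.0%.

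**The size under the planned analysis is unknown.** This also stands. The 3.31% and 3.79% are complete-data values, and the imputation figures come from a simpler model. The direction was the same in every setting tried.

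**A Z-test could mean the score test.** With the null variance it would give 2.09% and 2.34% at n=157. But Protocol 7.6 and SAP 9.4 and 9.5 decide on the confidence bound, the coverage in 9.5.1 matches Wald, and Wilson, which is the score interval, was considered and not chosen. If the score test was meant, the SAP has to say so.

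**Imputation needs the normal approximation.** SAP 9.5.1 itself ran Wilson with 15% missing data, and its reference 8 is, by its title, about Wilson intervals with multiple imputation.

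**Wilson is not exact, and a second rule could conflict with it.** Both are true. At n=150, H01 needs 122 with Wald (4.17%), 123 with Wilson (2.66%) and 124 with the exact limit (1.63%). The hierarchy between the two limits must therefore be written down.

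**Conclusion.** The concern holds. Under the rule in SAP 9.5, the lower-bound decision is not equivalent to a one-sided 0.025 test for either hypothesis. With complete data at n=157, the level is 3.31% for H01 and 3.79% for H02, about 1.3 and 1.5 times nominal (3.31/2.5 and 3.79/2.5), and it is above nominal at all 31 sample sizes from 130 to 160. In counts this is one success at n=157. It should be fixed because the plan states an alpha that its method does not deliver and the remedy is already in the SAP; it is not a threat to any clear-cut result. The conclusion rests on reading the planned interval as Wald, which the SAP's own coverage figures support, and on exact binomial calculation with independent subjects. The size under the planned imputation model remains to be shown.

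**What to change.** - **SAP 9.5 and Protocol 7.9.1:** decide H01 and H02 on the lower limit of the multiple-imputation Wilson interval of SAP reference 8, and report the Wald interval descriptively.
- **Exact check:** pre-specify a Clopper-Pearson lower limit on complete data. State that Wilson decides, that the exact limit is supportive, and that any disagreement will be reported.
- **SAP 9.5.1:** report one-sided rejection rates at 0.75 and 0.7874 under the planned imputation model.
- **SAP 6:** drop the claim of equivalence, or state the one-sided level actually achieved.

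The work is SAP wording and a short macro. The cut-off rises by one success at n=157; over n=130–160 it rises by one for H01 and by one or two for H02. Power at 85% true success:

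| | Wald | Wilson |
|---|---|---|
| H01, n=157, complete | 90.5% | 86.5% |
| H01, n=133, complete | 86.4% | 80.8% |
| H01, n=157, 15% missing, simple imputation | 86.1% | 80.2% |
| H02, n=157, complete | 59.4% | 50.6% |
| H02, n=157, 15% missing, simple imputation | 52.6% | 41.7% |

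The complete-data H01 power at n=133 equals that of the exact test on which the sample size was based, so the claim of more than 80% is kept there. Under imputation it is about 80% with no reserve (79.96% to 80.2% across runs). The larger loss falls on H02, for which the plan states no power.

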9.5.1 Adequacy of the Normal Approximation

A reasonable concern is that the success proportion will be close to 1 in this study, and it is unclear how well the normal approximation performs in this case. Using Monte Carlo simulation, performance of the normal approximation was evaluated. We generated 100,000 replications with either no missing data or 15% missing data (under a missing completely at random mechanism) with values that were subsequently imputed (10 imputations) using methods described elsewhere [8]. The population success proportion was set at 0.90 with 157 observations in each replication. Both in the absence of missing data and in the presence of missing data, the normal approximation yielded slight under-coverage relative the nominal level of 95%, 94.5% and 94.0%, respectively. By comparison, the Wilson method yielded slight over-coverage, 95.6% and 95.2%. Given these results, the normal approximation was chosen.

9.5.2 Sensitivity Analyses Incorporating Site Variation

In this study, implants are implanted within study sites and therefore may not be independent. Therefore, as a sensitivity analysis, a beta-binomial model will be used for incorporating possible between-site variability on implantation success [9]. In this model the number of implant successes (X_i) within each site follows a binomial distribution, $X_i | p_i \sim \text{Binomial}(n_i, p_i)$, with the proportion of successes (p_i) across sites following a beta distribution, $p_i \sim \text{Beta}(\mu, \theta)$ with $\mu = \alpha/(\alpha + \beta)$ and $\theta = 1/(\alpha + \beta)$ (where α and β are positive-valued parameters of the beta distribution). This is a random-effects model with a

mean success rate across sites (μ) that allows for variation by site (θ). The model is estimated using NLMIXED via the BETABIN SAS macro. In the absence of variation in the success rate across sites (i.e., $\gamma < .000001$, where $\gamma = \theta/(1 + \theta)$), the normal approximation to the binomial will be used. As noted in 9.8.4, the analysis is repeated in each imputed data set and thereafter aggregated.

9.6 Reporting of the Safety Endpoints

Survivorship of the GLOBAL ICON device at 24-, 60- and 120- months post-operative will be reported, where the device is deemed to be surviving if no humeral components (anchor plate, humeral head) have been removed for any reason. An estimate of device survivorship of the GLOBAL ICON implant will be presented using Kaplan-Meier methods. Removal of any component, defined as revision for any reason, is the event of interest. Cases not revised will be censored at their date of last follow-up, death (if a death occurred) or study end date. Survivorship point estimates and 95% confidence intervals will be presented for a time point if at least 40 subjects remain at risk. The conventional Greenwood estimate will be used to calculate the variance and the complementary log-log transformation will be used to construct 95% confidence intervals using PROC LIFETEST.

The type and frequency of all adverse events (AEs) in this study will be summarized, with distinction of serious AEs, operative and device related AEs. The type and frequency of AEs through 120 months post-operative will be presented in table form and via a listing. An overall summary of AEs will be provided, including the number and the percent of subjects with all AEs, all serious AEs, all related AEs (device and procedure related), and all AEs by severity. In addition, all adverse events, serious, and non-serious adverse events will be summarized and tabulated by preferred term, both overall and by severity, and by time period of onset.

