Protocol Title	GLOBAL ICON Stemless Shoulder System Post Market Clinical Follow Up Study
Protocol Number	CT 1401
Version Date	14MAY2020
Sponsor	Medical Device Business Services, Inc. (hereafter referred to as DePuy Synthes)
Study Device and Description	GLOBAL ICON Stemless Shoulder System. The intended use for the device, applicable to this study, is as follows: Candidates for total shoulder arthroplasty with severely painful and/or severely disabled Non-Inflammatory Degenerative Joint Disease (NIDJD) resulting from osteoarthritis (OA) or post traumatic arthritis.
Investigators and Sites	Up to 20 sites will be selected to participate in the study where the GLOBAL ICON Stemless Shoulder System is cleared for use.
Sample Size	A total of 157 subjects will be implanted with the GLOBAL ICON Stemless Shoulder System in Total Shoulder Arthroplasty (TSA). It is anticipated that attrition will be no greater than 15% at 24 months post-op, so that there will be at least 133 subjects with follow-up at 24 months for the primary endpoint analysis.
Study Design	Prospective, multi-centre, non-comparative, uncontrolled Post Market Clinical Follow Up (PMCF) Study. There is no control device.
Study Duration	Approximately 144 months total – 24 months of enrolment and 120 months of follow-up.
Visit Evaluations	Subjects will be evaluated preoperatively, at the time of surgery, immediately post operatively and at 3, 12, 24, 60 and 120 months post operatively
Primary Objective and Endpoint	
The primary objective of this PMCF study is to confirm device survivorship of the GLOBAL ICON stemless humeral component at 24 months post-operative.
 
The primary endpoint in this study is a composite success endpoint at 24 months post-operative, where an individual study subject is deemed to be a composite success if each of the following criteria is met at the 24 months follow-up visit:
 
 
• Radiographs indicate that there is no continuous radiolucent line around the GLOBAL ICON stemless humeral component
 
• The adjusted Constant-Murley score is greater than 85
 
• No GLOBAL ICON humeral component has been removed for any reason
 
• There have been no device-related serious adverse events
 

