**Relationship to study device or procedure should be rated as follows:**

**none** (definitely not related): there is no relationship between study device or procedure and the event.  
**possible** (remote possibility, possibly, or probably related): the relationship between study device or procedure could exist if there is no contradicting evidence that can reasonably explain the Subject's condition.

**definite** (definitely related): the relationship between study device or procedure and event does exist and is confirmed upon further investigation by the Investigator.

Pre-existing medical conditions or symptoms reported prior to device implantation are not to be recorded as AEs. In the event there is an exacerbation of the pre-existing medical condition or symptoms, then an AE must be reported.

AEs are reported beginning from implantation/operative procedure until subject participation has ended (study completed or consent withdrawn). AEs must be followed to resolution, or until the study completion or consent withdrawal. When a subject ends participating in the trial (either study completion or consent withdrawal), an AE must be designated either as "resolved" (end date must be provided), or as "ongoing."

Subjects should be encouraged to report AEs spontaneously and may volunteer AE information at any time. At each evaluation, the Investigator will determine whether an AE has occurred. If it is determined that an AE has occurred and is reportable, the Investigator should obtain all the information required to complete the appropriate AE form eCRF. If an event occurs at an outside institution, the Investigator should attempt to obtain, if possible, required AE information.

The Investigator will record the nature, severity, treatment and outcome of the AE, and will determine their association to the device or the study procedure.

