9.1 Descriptive Analyses

Study data will be tabulated for all subjects in the Safety Population using SAS version 9.4 or higher. Planned tabulations are described below and table, figure, and listing shells are provided separately (see Appendix).

Standard descriptive summaries for continuous data include the number of subjects with nonmissing data (n), mean, standard deviation (SD), median, minimum, and maximum values. For categorical data, the count and percentage will be provided. Percentages will be based on the number of subjects without missing data.

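### Adverse-event percentages through 120 months have no stated per-period denominator and no adjustment for incomplete follow-up; on a Safety Population denominator, late-onset events are understated

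*SAP*

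**What the plan says.** AE type and frequency is one of the two safety endpoints (protocol 3.4.2). SAP 9.6 sets the horizon: "The type and frequency of AEs through 120 months post-operative will be presented in table form and via a listing". The overall summary is a subject-level count, "including the number and the percent of subjects with all AEs, all serious AEs", followed by related AEs and AEs by severity. The detailed tables are "summarized and tabulated by preferred term, both overall and by severity, and by time period of onset". Protocol 7.9.2 plans the same outputs.

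On the denominator there are two general statements, neither specific to AEs:

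- SAP section 7: "Demographic data and analysis of the primary, safety, secondary and tertiary endpoints will be based on the Safety Population".
- SAP 9.1: "Percentages will be based on the number of subjects without missing data".

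On AE capture, the protocol (6.3, under the relationship ratings) says: "AEs are reported beginning from implantation/operative procedure until subject participation has ended (study completed or consent withdrawn". Protocol section 10 keeps subjects lost to follow-up out of the withdrawn category, and 5.6 allows that status to be documented at the end of the study.

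Other event-type outcomes are handled differently. SAP 9.6 analyses humeral component removal by Kaplan-Meier, with unrevised cases censored at last follow-up, death or study end. SAP 1.3 and 1.4 plan Kaplan-Meier for aseptic loosening and periprosthetic fracture, and 9.8.2 censors withdrawals at their last assessment.

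The only attrition figure is in the protocol synopsis: "It is anticipated that attrition will be no greater than 15% at 24 months post-op". Nothing is given for 60 or 120 months.

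**The concern.** Over ten years, follow-up will be unequal. A percentage of subjects with an event estimates risk only if every subject in the denominator could have had the event recorded. A subject last seen at month 12 has no AE record for months 60 to 120. If that subject stays in the denominator, the table treats the absence of a record as the absence of an event.

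The later the onset period, the more such subjects there are, and the error is in the favourable direction. The 60- and 120-month visits exist to detect late events, so this is where the tables should be most reliable.

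The SAP recognises the problem elsewhere. It censors removal, loosening and fracture. For the 24-month composite it treats the device-related serious AE status of an early leaver without a recorded failure event as unknown and imputes it (9.8.1, 9.8.5). The AE tables give the same events no such treatment.

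The interim analysis for a US marketing application (protocol 7.10) includes safety summaries. If its data cut falls before all subjects have completed the later periods, percentages on everyone treated would be diluted even without dropout.

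**Working it through.** **1. The plan's own figures.** Evaluable N is 133 and attrition is 15%: 133 / 0.85 = 156.5, rounded up to 157. In reverse, 157 × 0.85 = 133.45, so about 133 are still followed at 24 months. These figures reproduce. No AE rate is stated, so there is none to reproduce.

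**2. Simple comparison at the stated ceiling.** Take 10 subjects with an event after month 24 (an illustrative count).

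- All treated: 10 / 157 = 6.4%.
- Still followed at month 24: 10 / 133 = 7.5%.
- Ratio: 133 / 157 = 0.85.

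The ratio is simply the retention fraction. The two figures also answer different questions: the first is the share of all treated subjects with an observed late event, the second the observed share among those who reached month 24 under follow-up. With 25% or 40% lost (assumed), the same arithmetic gives 10 / 117.75 = 8.5% or 10 / 94.2 = 10.6%.

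**3. Like-for-like comparison under an illustrative model.** Assumptions: constant hazard of a first event of one AE type; non-fatal loss independent of event risk; 10-year risk R = 10%.

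- Event hazard: λ = −ln(1 − R)/10 = −ln(0.90)/10 = 0.0105 per year.
- Loss hazard to 24 months, from the stated 15%: h = −ln(0.85)/2 = 0.0813 per year.
- Observed crude proportion over an interval from a to b with constant hazards: λ/(λ+h) × [exp(−(λ+h)a) − exp(−(λ+h)b)], applied piecewise with a separate loss hazard after month 24.
- First-event risk without loss, months 60–120: exp(−5λ) − exp(−10λ) = 4.87%.
- Risk in months 60–120 given event-free at month 60: 1 − exp(−5λ) = 5.13%.

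Loss after month 24 is assumed in all three rows.

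| Loss after 24 months | Under follow-up at 60 months, of 157 | Crude % through 120 months (target 10%) | Crude % for onset 60–120 on 157 (target 4.87%) | Onset 60–120 on at-risk denominator (target 5.13%) |
|---|---|---|---|---|
| None | 133 | 8.65% | 4.14% | 5.13% |
| 30% total by 120 months | 124 | 8.05% | 3.63% | 4.84% |
| Same hazard continues (56% lost by 120 months) | 105 | 6.89% | 2.67% | 4.22% |

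The at-risk denominator here is subjects still followed and event-free at month 60.

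For 10-year risks from 5% to 20%, the ratio of reported to target value is about 0.69–0.87 through 120 months on 157, 0.55–0.85 for onset in months 60–120 on 157, and 0.82–1.00 for that period with at-risk denominators. Changing the denominator removes much of the understatement. The remainder comes from loss within the period, which person-years and cumulative incidence address.

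**4. Deaths.** A subject who has died cannot have a later event. Keeping that subject in the denominator gives a valid cumulative incidence with death as a competing event. An AE that leads to death is itself a serious AE under protocol 6.3. The calculation therefore covers non-fatal loss only.

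**The case against.** **The denominator is not written down.** SAP 9.1 bases percentages on subjects without missing data, and protocol section 10 lists subjects who do not return as missing data. Read together, these could exclude lost subjects from late periods. The table shells, where this would normally be settled, are a separate document that was not available. This stands: a reader might infer that the plan states that leavers are counted as event-free, and it does not. But the 9.1 rule does not resolve the matter, because an AE that was never reported leaves no missing field, and the only population named for safety analyses is the Safety Population.

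**AE capture is broad.** Protocol 5.3 collects AEs at every contact and includes care by others where source records are available; 6.3 asks for information on events at outside institutions. A missed visit alone does not end capture. This stands for missed visits, but not for subjects with whom contact has ceased.

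**The main late device events are covered.** Removal, humeral loosening and periprosthetic fracture have Kaplan-Meier estimates. This stands and narrows the point. Serious AEs as a class, device-related AEs, serious adverse device effects, and late infection or dislocation (both in the protocol 6.1 risk list) have none.

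**The consequence is limited.** There is no comparator, no safety hypothesis is tested, and SAP section 6 rules out labelling claims from safety endpoints. This also stands. It makes this an inexpensive improvement to descriptive reporting and not a threat to the trial's main conclusion.

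**Conclusion.** The point holds in a limited form. AE frequency over ten years is planned as simple percentages, by undefined onset periods, with no per-period denominator and no allowance for incomplete follow-up. If the Safety Population is the denominator, as the analysis-set text implies, late-onset percentages are understated for subjects lost to follow-up.

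The only size anchored in the documents is the 15% ceiling at 24 months: 6.4% against 7.5% for 10 late events. Everything larger depends on assumed later loss. It would be wrong to infer that late rates are 15–40% too low. That range restates assumed loss of 15–40% and compares two different quantities. It would also be wrong to count deaths as part of the bias.

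The like-for-like illustration rests on constant hazards and independent loss. If subjects who leave have a different event risk, neither an at-risk denominator nor censoring fully corrects for it. The sample size and the primary test are unaffected.

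**What to change.** In SAP 9.6 and the table shells:

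1. Define the onset periods in days from surgery.
2. For each period, use as denominator the subjects still under follow-up at its start, and print that number. Base follow-up on the date of last contact or assessment, not on withdrawal status, because subjects lost to follow-up are not classed as withdrawn.
3. Show person-years of follow-up per period.
4. Add cumulative incidence of first serious AE, first device-related AE and first serious adverse device effect, with 95% confidence intervals at 24, 60 and 120 months. Censor at last follow-up, and treat death as a competing event where it is not itself the event. Apply the SAP's existing rule of at least 40 subjects at risk. For serious AEs that rule may suppress the 120-month estimate, since subjects leave the risk set at their first event.
5. Keep the crude counts, overall percentages and listing, with the denominator stated in each table.

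Protocol 7.9.2 should carry a matching sentence.

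The cost is SAP and shell wording and a few extra outputs. Onset dates and follow-up dates are already collected, so no new data are needed. Late percentages will look somewhat less favourable.
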